5 BACKGROUND AND RATIONALE

5.1 Background

Levosert®is a levonorgestrel (LNG)-releasing intrauterine system (IUS) containing 52 mg of levonorgestrel. When inserted into the uterus, it slowly releases this hormone to be absorbed by the user. The initial release of levonorgestrel is approximately 20 micrograms per day. This rate decreases progressively to approximately 8.6 micrograms/day after 6 years. The average in vivo release rate of LNG is approximately 14.3 micrograms/day over a period of 6 years.

In Europe, Levosert is indicated for use in 1) contraception and 2) heavy menstrual bleeding, hereafter referred to as menorrhagia or HMB.

- 1) Contraception. Levosert prevents pregnancy by thinning the lining of the uterus, by making the normal mucus in the opening of the uterus thicker, so that the sperm cannot get through to fertilise the egg and by preventing ovulation in some women.
- 2) Treatment of menorrhagia. The hormone in Levosert acts by thinning the lining of the uterus, so that there is less bleeding every month.

Levosert was first authorised in Europe via Decentralised Procedure (DCP; licence number UK/H/3030/001/DC) on 28 Dec 2012 for the treatment of menorrhagia for three years. Countries targeted for the proposed study (Czech Republic, Poland, Serbia, and Slovakia) authorized Levosert for the treatment of menorrhagia in a separate DCP (HU/H/0580/001/DC) in 2013. The applications were based on a therapeutic equivalence study conducted with Levosert and Mirena®. On 16 Oct 2014, the second indication 'contraception' was approved with new supportive data from the ongoing pivotal Phase 3 study M360-L102. Since then and based on the results of the same Phase 3 study, the duration of use of Levosert for use in contraception extended to 5 years, then to 6 years in all European countries where the product is marketed. However, the ongoing Study M360-L102 was designed to evaluate contraceptive efficacy only (not menorrhagia), and thus, there is need for further evidence regarding usage for the menorrhagia indication to support its use up to the recommended duration determined for the contraception indication.

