10.1 Primary Endpoint Definition

The primary objective of this study is to describe the expected real-world usage duration of Levosert for its different indications.

Duration of Levosert usage is defined as the difference in time between removal (with or without replacement) and insertion of the device. In the absence of detailed patient-level data and in the context of this survey, expected duration of Levosert usage for each indication will be calculated as follows:

Expected usage duration of Levosert (years)

$$= \sum_{i=1}^{6} (i \ x \ likelihood \ of \ Levosert \ removal \ in \ Year \ i)$$

+ (likelihood of Levosert removal beyond Year 6 x total expected usage duration in those patients)

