10.3 Data Analysis

All analyses will be descriptive in nature. Categorical variables will be summarized using counts and percentages. Continuous variables will be summarized using the number of observations (n), mean, standard deviation (SD), median, minimum, and maximum, interquartile ranges (IQR), and 95% confidence intervals (CI), as appropriate. In addition, utilization patterns of Levosert will be visualized using plots or similar techniques.

1. Geographical distribution of Prescribers (by country)

- 2. Count and percentage of Prescribers by ranges of their professional time spent on direct patient care
- 3. Count and percentage of Prescribers by duration of their medical practice
- 4. Count and percentage of Prescribers by practice setting
- 5. Count and percentage of Prescribers having prescribed each brand of levonorgestrel IUS
- 6. Count and percentage of Prescribers having experience removing each brand of levonorgestrel (with or without replacement)
- 7. Descriptive statistics on Prescribers' count of IUS prescriptions in the past 10 years
- 8. Descriptive statistics on Prescribers' count of Levosert prescriptions and removals (with or without replacement), by indication
- 9. Descriptive statistics on Prescribers' count of patients they personally manage in a typical month without COVID-19 restrictions
- 10. Descriptive statistics on percentage of Prescribers' patients by type of contraception, by indication
- 11. Descriptive statistics on percentage of Prescribers' patients using IUSs who are receiving Levosert, by indication
- 12. Distribution of Prescriber's patients at the time of Levosert prescription among age categories, by indication
- 13. Count and percentage of Prescribers among categories of duration-of-effectiveness of Levosert for heavy menstrual bleeding
- 14. Percentage of Prescribers' patients getting Levosert removed by the end of each year, by indication
- 15. Descriptive statistics on the total duration of use of Levosert in patients who use Levosert for more than six years, by indication
- 16. Percentage of Prescribers' patients who use Levosert for heavy menstrual bleeding indication who would continue to show treatment effectiveness by the end of each year
- 17. Distribution of Prescribers' patients among reason-for-removal categories, by indication
- 18. Count and percentage of Prescribers by overall level of satisfaction with Levosert in patients who use it for three or more years, by indication

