By the end of Year 6	%	%

VALIDATION MESSAGE REQUIRING TRANSLATION:

ERROR: Please note your responses for each column must be cumulative. For example, your response for the end of year 2 must be equal to or greater than your response for the end of year 1, etc.

Q8. For patients who use **Levosert (levonorgestrel)** for **contraception only** for more than six years, for approximately how many years in total do these patients typically use **Levosert (levonorgestrel)**?

Please feel free to provide a fractional number of years.

	# of years	RANGE 7-10
--	------------	------------

Q9. For patients who use **Levosert** (**levonorgestrel**) for **heavy menstrual bleeding** (with and without **intended contraception**) for more than six years, for approximately how many years in total do these patients typically use **Levosert** (**levonorgestrel**)?

Please feel free to provide a fractional number of years.

	# of years	RANGE 7-10
--	------------	------------

13-02-2023

Q10. Among your patients using Levosert (levonorgestrel) for heavy menstrual bleeding (with and without intended contraception), what percentage would continue to show treatment effectiveness by the end of each year (cumulatively since insertion), while continuing to use the same Levosert (levonorgestrel) device.

Please note your responses must be cumulative over time since insertion.

Treatment effectiveness is defined as significant reduction in menstrual blood loss.

		Heavy menstrual bleeding (with and without intended contraception)
1	By the end of Year 1	%
2	By the end of Year 2	%
3	By the end of Year 3	%
4	By the end of Year 4	%
5	By the end of Year 5	%
6	By the end of Year 6	%
7	Beyond 6 years	%

VALIDATION MESSAGE REQUIRING TRANSLATION:

ERROR: Please note your responses for each column must be cumulative. For example, your response for the end of year 2 must be equal to or less than your response for the end of year 1, etc.

Q11. Considering **all** your patients ever having used and/or currently using **Levosert (levonorgestrel)** for the following indications and who had it removed (with or without replacement), approximately what percentage of these patients had **Levosert (levonorgestrel)** removed for each of the following reasons?

	Contraception only	Heavy menstrual bleeding (with and without intended contraception)
Removed per Schedule (IUS Expiry)	%	%
Planning for family	%	%
Side effects	%	%
Lack of effectiveness	%	%
Menopausal	%	%
Other (specify)	%	%
Total	100%	100%

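### Q8 and Q9 ask about use beyond six years and invite fractions, but accept only 7 to 10, so a prescriber whose typical value lies between 6 and 7 years cannot report it

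*Protocol*

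**What the plan says.** Appendix 3, Q7 asks each prescriber, by indication, for the cumulative percentage of patients whose device has been removed by the end of each year. The last row is "By the end of Year 6". Whatever is left of 100% is the group with use beyond six years.

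Q8 and Q9 then ask about that group, one question per indication: "for more than six years, for approximately how many years in total do these patients typically use" the device. Both add: "Please feel free to provide a fractional number of years". In both, the field carries the check "of years RANGE 7-10".

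The answer is used twice:

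- Section 10.1 makes it part of the last term of the primary formula: "likelihood of Levosert removal beyond Year 6 x total expected usage duration in those patients".
- Section 10.3, item 15, reports it separately: "Descriptive statistics on the total duration of use of Levosert in patients who use Levosert for more than six years, by indication".

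Section 10.1 also states what is being measured: "Duration of Levosert usage is defined as the difference in time between removal (with or without replacement) and insertion of the device". The protocol gives no reason for a lower limit of 7.

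**The concern.** The group asked about starts just above 6 years and the entry field starts at 7. The interval between them belongs to the group, is invited by the request for fractions, and cannot be entered. No other item captures it.

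The interval is a plausible place for answers. Section 5.1 says contraceptive use was extended to 5 years, "then to 6 years in all European countries where the product is marketed", and Q11 lists scheduled removal at expiry among the removal reasons. Removal some weeks or months after the six-year mark would put a patient in this group with a duration well short of 7.

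A floor of this kind can move the result in one direction only, towards longer use, in a study commissioned because data on longer use in heavy menstrual bleeding are lacking. It acts on the primary endpoint and on item 15, whose reported minimum cannot fall below 7 whatever prescribers have seen. It cannot be undone after fielding, because the refused values are never recorded.

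**Working it through.** The protocol states no expected-duration figure, so there is none to reproduce. The check applies its own formula.

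**Inputs**

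- Formula (Section 10.1): E = Σ i × P(removal in Year i) for i = 1 to 6, plus P6 × T. P6 is the share beyond Year 6 and T is the Q8 or Q9 answer.
- Accepted T (Appendix 3): 7 to 10. Group asked about: T above 6.
- Retention at Years 1 to 5 (Appendix 1, from a post-marketing study of LNG-IUS users): 0.94, 0.87, 0.82, 0.76, 0.65. Used only for illustration.
- P6 is not given. Assumed range: 0.10 to 0.50.

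**Step 1: the overstatement.** If the true typical value is T < 7 and at least 7 must be entered, only the last term changes:

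overstatement in E ≥ P6 × 7 − P6 × T = P6 × (7 − T)

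For item 15 it is at least 7 − T, which is under one year if the minimum of 7 is entered. If T ≥ 7, both are zero.

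**Step 2: size for a prescriber whose T is below 7, entering 7**

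| P6 (assumed) | T = 6.5 | T = 6.1 |
|---|---|---|
| 0.10 | 0.10 × 0.5 = 0.05 | 0.10 × 0.9 = 0.09 |
| 0.30 | 0.30 × 0.5 = 0.15 | 0.30 × 0.9 = 0.27 |
| 0.50 | 0.50 × 0.5 = 0.25 | 0.50 × 0.9 = 0.45 |

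For item 15 the corresponding overstatement is 0.5 years (T = 6.5) or 0.9 years (T = 6.1).

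**Step 3: the whole formula.** The retention figures give removal probabilities of 0.06, 0.07, 0.05, 0.06 and 0.11 in Years 1 to 5, and 0.65 − P6 in Year 6. Years 1 to 5 contribute 0.06 + 0.14 + 0.15 + 0.24 + 0.55 = 1.14. Year 6 contributes 6 × (0.65 − P6).

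| P6 | Years 1–6 | E with T = 6.5 | E with T forced to 7 |
|---|---|---|---|
| 0.10 | 1.14 + 3.30 = 4.44 | 5.09 | 5.14 |
| 0.30 | 1.14 + 2.10 = 3.24 | 5.19 | 5.34 |
| 0.50 | 1.14 + 0.90 = 2.04 | 5.29 | 5.54 |

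The differences match Step 2.

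**Step 4: can devices be in the 6-to-7-year window at all?** Summing the four countries in Table 2, sales were 142 (2014), 11,571 (2015), 15,337 (2016) and 15,778 (2017). Assume insertion at sale, even sales within each year, and fielding in mid-2023 (the protocol is dated 13-02-2023). Devices old enough to have passed six years: 142 + 11,571 + 15,337 + 15,778/2 = 34,939. Old enough to have reached seven: 142 + 11,571 + 15,337/2 ≈ 19,382. The difference, 15,557, is about 45% of the first figure. Those devices could not yet have reached the lowest permitted answer. This concerns attainable age only. It ignores earlier removals and says nothing about when devices are actually removed.

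**The case against.** **One value per prescriber, not per device.** A reader might infer that every device removed between 6 and 7 years has to be entered as at least 7. The documents do not support that. No device-level data are collected, and Q8 and Q9 each take one approximate typical figure. If half of a prescriber's long users average 6.4 years and the other half 7.6, and typical is read as the mean, the answer is (6.4 + 7.6)/2 = 7.0. That is accepted as it stands and causes no error. This objection holds: the floor binds only when the prescriber's own typical value is below 7.

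**The formula already works in whole years.** Section 10.1 scores a removal in Year i as i years, so a removal at 5.1 years counts as 6. On that scale a removal in the seventh year would count as 7, which matches the floor. This stands in part. The protocol does not give it as the reason, and it does not fit the invitation to enter fractions or the definition of duration as time from insertion to removal. It does mean that lowering the floor leaves the rounding in Years 1 to 6 untouched.

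**A larger size cannot be read off Appendix 1.** A reader might put the 65% retention figure into the last term and get an overstatement of almost half a year (0.65 × 0.75 = 0.49 at T = 6.25). But 65% is retention at Year 5. Using it as the share beyond Year 6 assumes no removals in Year 6, the year in which the stated contraceptive duration ends.

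**Timing after six years is not documented.** This is correct, and the argument from the six-year duration applies to contraception. For heavy menstrual bleeding, Section 5.1 gives a first authorisation for three years and a need for further evidence on longer use, so clustering just after six years is less well supported there. The refusal of values between 6 and 7 is the same in both questions.

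**Conclusion.** The mismatch is certain: Q8 and Q9 refuse values that belong to the group they ask about. Its effect is conditional. For a prescriber whose typical value T is below 7, expected duration is overstated by at least P6 × (7 − T). Over an assumed P6 of 10% to 50%, that is 0.05 to 0.25 years at T = 6.5 and 0.09 to 0.45 years at T = 6.1. Item 15 is overstated by at least 7 − T for that prescriber. For all others the effect is zero. How many prescribers are affected is unknown, so no figure for the overall study estimate can be given.

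The sizes rest on assumed values of P6 and T, neither of which the protocol supplies. The direction does not depend on them.

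A reader might also infer that prescribers with no patients beyond six years would distort the primary endpoint by being made to supply a figure. They would not: if Q7 reaches 100% at Year 6, the last term is zero. Only item 15 could be affected, and the protocol does not say whether an answer is mandatory. The point deserves correction before fielding, but it does not undermine the primary analysis as a whole.

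**What to change.** In the survey program, before fielding, change the accepted range in Q8 and Q9 to greater than 6 up to 10, decimals allowed. Optionally, and for the sake of item 15 only, do not require an answer to Q8 or Q9 when the Year 6 entry in the matching Q7 column is 100%.

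This removes the floor in the last term. It does not make the formula free of rounding, and the report should say that removals in Years 1 to 6 are scored as whole years.

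The cost is one validation limit and, if taken up, one routing rule. No further data or respondents are needed. Section 11.2 requires ethics committee approval of questionnaire amendments in each country, while Section 12.2 exempts purely logistical or administrative changes such as inconsistencies. The sponsor should settle which applies and notify or seek approval accordingly.
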